Involvement of Primary Care Providers (PCPs): The effects of asthma self-management in controlling and reducing the burdens of the disease can be augmented when self-management activities are coordinated in collaboration with a healthcare provider. Having recognized the important roles that the healthcare providers play in adolescents' asthma self-management, we will attempt to incorporate the clinical system in our programs. For both groups, each subject's primary care provider (PCP) will be informed of the teen patient' study participation and training content in an introductory letter which will be either mailed or faxed to the office. The PCPs will also receive written bi-annual reports from the study team that summarizes the levels of asthma control and medication adherence of their teen patients in the past 6 months. In addition, we will communicate to the PCPs via letter or phone call when research data (e.g., FEV1 < 60% predicted, uncontrolled symptoms, consistent medication non-adherence, recent ED visit) warrant clinical attention. The timing and content of such reports provided to the PCPs (except for the introductory letter) will be documented and taken into consideration in analyzing and interpreting research data. Subjects will be encouraged to communicate with their PCP about their asthma conditions learned through symptom monitoring (e.g., symptom diary, PEFR) during their scheduled or unscheduled office visits.

Measures: Sources of research materials will include standardized questionnaires, demographic form, peak flow meters, spirometry, CMS/TennCare database and medical records. Data from these sources will be collected with parents'/participants' consent and according to the standard procedure approved by the IRB. All data will be used for research purposes only and will be kept confidential and anonymous by using subject IDs without identifiers. Only the PI and authorized research staff will have access to these data.

Primary Outcome:

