6. REPORTABLE EVENTS

Adverse events (AEs) are defined as physical and psychological discomfort (boredom, fatigue, stress) related to completing multiple questionnaires and participating in the day camp program, intense self-management training/program. AEs will also include physical injuries during recreational activities at the camp. Any breach of confidentiality would also be an adverse event. These events are believed to be possible but are not automatically expected. Procedures will be implemented in order to prevent and address AEs during the study

Mechanism for Reporting Adverse Effects. The project staff will also periodically inquire about adolescents' reactions or feelings throughout the study. The project staff will report any AEs observed in relation to study participation to the site-PI and PI immediately. Review of adverse events will include: (1) Adverse events in aggregate, by attribution (expected or unexpected) and relationship to study intervention, (2) Whether the study accrual pattern warrants continuation/action, and (3) potential protocol violations. The PI will also monitor study safety by

weekly reviews of randomly selected cases for research staff's adherence to study procedure and IRB compliance (e.g., informed consent). The PI will continuously evaluate risks associated with research procedure and maintain subject confidentiality through weekly team meetings and conference calls with the project staff in other sites. The center coordinator will assist the PI in reviewing, capturing and reporting any adverse events and unanticipated problems to the IRB and NINR using interactive computer modules in the Clinical Data Management System. The PI will assess any external factors or relevant information that may impact the safety of participants or ethics of the study.

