7. RISK/BENEFIT ASSESSMENT

Risks to Subjects

Potential Risks: This study will present minimal potential risks to subjects. Data will be collected primarily using questionnaires and noninvasive physiological measures (peak flow meters and spirometer). However, a small number of subjects may be stressed by having to complete multiple questionnaires every 3 months and monitor peak flow values daily during study participation. Due to the intensive nature of peer leader training and the camp education program, subjects may experience either fatigue and/or boredom. In addition, peer leaders may experience emotional distress potentially associated with their dealings with camp participants' psychological and behavioral issues as well as any issues related to the illness during bimonthly contacts. Also, injuries may also occur during participation in camp recreational activities. The likelihood of risks associated with the camp program, however, is minimal given the sufficient number of trained adult volunteers and the study staff who will closely monitor the conditions and the safety of camp participants during the camp.

Psychological/Physical Distress: To avoid worsening of physical or emotional preconditions, we will exclude those who have serious health (other than asthma) and emotional preconditions (e.g., severe depression, anxiety disorders, schizophrenia) as indicated in the eligibility criteria. Adult nominators (clinicians, teachers, etc.) of peer leaders will be informed of this eligibility criterion. For regular participants, the coordinator will confirm these criteria with parents. Adolescents and parents will be assured that, if the adolescent's responses demonstrate a risk to themselves or others, the adolescent's primary care provider or the family will be notified immediately.

This study involves minimal risk to participants as the study procedures are noninvasive in nature and do not require any changes in existing treatment regimens. Should the research team identify any participant with serious asthma symptoms that have not received proper treatment, we will encourage the subject to seek medical attention immediately or refer the subject to his/her primary care provider if known. The research team will hold weekly multi-site standing meetings to review participants' responses to the intervention and discuss any challenges or issues encountered in working with the participants.

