Confidentiality: To ensure confidentiality, subjects will be assigned an identification number, and they will be informed that all information will be held in confidence. Hardcopy data will be kept in a locked file cabinet in each site's project office. Subject information connecting subject names with identification numbers will be locked in a separate file drawer in each site-PI's office. Any printed subject information will be kept in the three site-PIs' locked drawers and will be shredded immediately if not used. Subjects will be informed that their parents or guardians will not have access to their responses for any of the measures. Adolescents and parents will also be assured that forms will be destroyed safely upon completion of the study. Parents and adolescents will be informed that only the research team, University IRB members, grant sponsors and auditors from NIH will have access to their responses. All data from any parent or adolescent requesting withdrawal from the study will be destroyed at the time of the request. Only aggregated data without any personal identifiers will be reported in publications or presentations.

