9. RESEARCH INFORMATION IN MEDICAL RECORDS

N/A

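### Families are to be told that only four named parties see teens' responses, yet the plan sends each teen's primary care provider routine reports and alerts built largely on those responses

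*Combined protocol and SAP*

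**What the plan says.** Three statements limit who may see the data.

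- Section 7 (Confidentiality), repeated in Section 8, sets out what parents and adolescents will be told: "only the research team, University IRB members, grant sponsors and auditors from NIH will have access to their responses". Both sections add that parents will not be able to see the answers on any measure.
- Section 4.1 (Measures) lists questionnaires, peak flow, spirometry, claims and medical records as sources and then says: "All data will be used for research purposes only and will be kept confidential and anonymous by using subject IDs without identifiers".
- The same paragraph closes: "Only the PI and authorized research staff will have access to these data".

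Two statements send information outside those limits.

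- Section 4.1 (Involvement of Primary Care Providers), for both arms: "The PCPs will also receive written bi-annual reports from the study team that summarizes the levels of asthma control and medication adherence". It adds a letter or call to the provider when study findings call for it; the examples are an FEV1 under 60% of predicted, uncontrolled symptoms, persistent non-adherence and a recent emergency visit.
- Section 7 (Psychological/Physical Distress) says families will be assured that, if a teen's answers point to danger to the teen or to someone else, "the adolescent's primary care provider or the family will be notified immediately".

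**The concern.** The access statements are phrased as exclusive, and none of them includes the primary care provider. The provider communications are nevertheless a standing part of the study: they run in both arms, their timing and content are to be logged, and they are to be considered in the analysis.

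What is at stake is participant protection. Minors are asked for candid reports of missed medication under a statement about recipients that the plan itself contradicts. Section 7.2 rests its risk/benefit judgement partly on confidentiality being carefully explained and handled. Staff who read Sections 7 and 8 and staff who read Section 4.1 would also give families different answers to the same question.

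**Working it through.** The plan gives no figure to reproduce. The check sets the statements side by side.

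1. **Who is on the list.** Sections 7 and 8 name the research team, the university IRB, the grant sponsors and NIH auditors. Section 4.1 (Measures) names the principal investigator and authorized staff. The provider is on neither list.

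2. **What the provider receives.** The report "summarizes the levels of asthma control and medication adherence of their teen patients in the past 6 months". A summary of a provider's own patients is read most naturally as patient-level, and a letter or call about one teen's results cannot be anything else. Such communications identify the teen and serve care, so they fit neither the anonymity nor the research-only wording in Measures.

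3. **Whether the content is the teen's responses.** The outcome list in Section 4.1 settles most of this.
   - Adherence: the self-report scale and missed-dose question are given at every assessment. Dose counts are taken only at baseline and 15 months. A summary between those points must use self-report.
   - Asthma control: the Asthma Control Test is a 5-item questionnaire.
   - Emergency visits: the exacerbation checklist is self-report at all time points, although claims and records are a second source.
   - FEV1: this is measured by spirometry, so it is not a response. Its disclosure conflicts with the Measures access sentence, which covers spirometry, rather than clearly with the promise in Sections 7 and 8.

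4. **Whether the disclosed exception covers it.** The Section 7 assurance is triggered by danger to the teen or others. Its wording does not reach a scheduled summary, non-adherence as such, a low FEV1 or a recent emergency visit. It also sits uneasily with the statement that parents see no answers on any measure, because it allows the family to be notified on the basis of answers.

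5. **Scale, for orientation only.** The number of reports per teen is not stated. Assume one every 6 months: 15 / 6 = 2.5, so 2 complete reports over the 15 months after camp; 21 / 6 = 3.5, so 3 over the 21 months of data collection given in Section 7.2. For the number of teens, use 378 enrolled, or 276 if the planned 27% attrition occurs (378 × 0.73 = 275.9).
   - Low: 276 × 2 = 552 reports.
   - High: 378 × 3 = 1,134 reports.
   - Event-driven letters and calls would be additional; the plan gives no basis for counting them.

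**The case against.** The strongest reply is that a summary sent to a clinician is not access to responses, that the provider contact is openly part of the protocol, and that the consent forms may explain it.

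- **Summary versus access.** A narrow reading of the promise in Sections 7 and 8 is possible. It does not rescue the Measures sentences, which cover all the data and are limited to research use. It is also not how a teen would hear an assurance about who sees the answers, when the interim summary largely passes on those answers.
- **Consent and assent.** These forms were not available for review, so it cannot be said that families are never told of the reports. What can be said is that the protocol's own account of what they will be told is inaccurate. This part of the objection stands.
- **Risk notification.** Families are told of this exception, so a notification within it breaks no promise. This also stands.

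Three stronger inferences are tempting, and the documents do not support them.

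- *Alerts are blocked, leaving a safety gap.* Nothing forbids an alert. Section 4.1 directs provider communication, and Section 7 directs notification, referral of untreated serious symptoms, and a staff protocol for informing family and provider.
- *Every report is an adverse event, so event counts cannot be interpreted.* Section 6 says "Any breach of confidentiality would also be an adverse event" but does not define a breach. Treating a protocol-specified communication as one adds a definition the plan does not contain.
- *The not-applicable entry in Section 9 is a further contradiction.* A letter to a provider's office is not clearly the study placing research information in a medical record.

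**Conclusion.** The contradiction is in the current text and holds in this form: the access statements in Sections 4.1 (Measures), 7 and 8 leave out the provider reports and alerts that Section 4.1 plans, and the risk exception in Section 7 does not fill the gap. Following the plan as written means giving parents and minors an incorrect statement about who receives their information.

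It applies in principle to all 378 teens in both arms. It affects participant protection and the accuracy of the consent process as described; it alters no estimate, test or sample size. The conclusion assumes that the provider reports are patient-level, which is the natural reading. The range of 552 to 1,134 reports rests on the assumed frequency and retention, and nothing in the conclusion depends on it. The matter should be corrected, and the correction is one of wording.

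**What to change.** - In Sections 4.1 (Measures), 7 (Confidentiality) and 8, name the teen's primary care provider as a recipient of the twice-yearly summaries and of the letters or calls, and qualify the anonymity and research-only wording to match.
- In the same places, cross-refer to the Section 7 risk exception (provider or family), and reconcile it with the statement that parents have no access to answers.
- Check that the consent and assent forms say the same, and amend them if they do not.
- In Section 6, state that these planned disclosures are not breaches of confidentiality.

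No alert criterion or clinical rule needs to change. The cost is one wording amendment through the IRB. Teens who know that their provider receives a summary may report adherence more guardedly; because both arms receive the reports, this should apply equally to each.

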7.3 Alternatives to Participation

There are no alternative courses of action should the subject elect not to participate in the study.

8. CONFIDENTIALITY OF DATA AND INFORMATION STORAGE

To ensure confidentiality, subjects will be assigned an identification number, and they will be informed that all information will be held in confidence. Hardcopy data will be kept in a locked file cabinet in each site-PI's office. Subject information connecting subject names with identification numbers will be locked in a separate file drawer in each site-PI's office. Any printed subject information will be kept in the three site-PIs' locked drawers and will be shredded immediately if not used. Subjects will be informed that their parents or guardians will not have access to their responses for any of the measures. Adolescents and parents will also be assured that forms will be destroyed safely upon completion of the study. Parents and adolescents will be informed that only the research team, University IRB members, grant sponsors and auditors from NIH will have access to their responses. All data from any parent or adolescent requesting withdrawal from the study will be destroyed at the time of the request. Only aggregated data without any personal identifiers will be reported in publications or presentations. Only two documents, the informed consent form and the subject contact form, will contain participant's identifying information. The informed consent form will be kept separate from the de-identified subject data, in paper form, accessible only to the essential study team. The contact form, containing the participant's contact information (i.e., address and cell/phone numbers), will be needed by the study coordinator/peer leaders for follow-up visits for data collection.

Informed consent documents, with identifying information (e.g. subject's name) and a link to the unique subject ID code, will be kept in a locked, secure location accessible only to the essential members of the study team. The contact information form, used by the study coordinator to

contact participants to arrange follow-up assessment visits will be stored separate from the research database on a password-protected secure server maintained by the University of Rochester School of Nursing IT Department.

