2. CHARACTERISTICS OF STUDY POPULATION

2.1 Subject Characteristics

Asthma and its morbidity disproportionately affect minority children of low-income families in inner cities, where asthma severity has increased and poses serious challenges to achieving adequate asthma control.⁵ Disparate burdens of asthma and its adverse outcomes among minority children have been consistently documented in the past 20 years.^{4, 23-25} In 2010, asthma prevalence in black children under 18 years was twice that of white youths; children in families below the poverty threshold as defined by the US Census Bureau were 1.5 times more likely to report current asthma than those in families at or above 200% of the poverty line.² Compared with white youth, black inner-city children are 4 and 3 times more likely to have asthma-related ED visits and hospitalizations respectively.⁴ The three cities where the study will take place, Buffalo, NY; Baltimore MD; Memphis TN demonstrate high rates of pediatric asthma, high health care utilization and high morbidity and mortality rates, thus this study will take place in these cities that are most likely to benefit from a proposed intervention.

a) Number of Subjects:

A total of 378 adolescents (12-17 years) and 42 adolescent peer leaders (16-20 years) will be recruited for this study. The sample size (N=378) is based on the power analysis using a novel method developed by Roy et al.²⁶ for a 3-level hierarchical longitudinal design based on the program "RMASS." This method has the advantage of incorporating three levels from the sites and repeated-measures from each subject with random-effects of the time trends at both the subject- and site-level, which are assumed to be equivalent in terms of sampling proportions, number of groups and differential attrition rates over time. In this proposed study, quality of life, the primary outcome, was used to estimate the sample size. Using data from the previous study,²⁷ the longitudinal trajectories of quality of life and its treatment-by-time interactions based on subject-level randomization were modeled: the estimated treatment*time interaction coefficient was 0.6 units, estimated SDs for error was 15, and the random-slope was 1.76. These estimated values with a Type-I error rate (alpha) of .05 yielded a total sample size of 276 that would detect a

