to, and they are free to withdraw from the study at any time. The coordinator will solicit and answer any questions. When all questions have been answered, the coordinator will ask the subject a couple of questions pertaining to study procedure and the content of the consent to ensure the subject's understanding. For Spanish-speaking parents, the consent form will be prepared in their language, and an RA who is fluent in Spanish will assist obtaining the consent following the procedure described above. A parent/guardian will be asked to sign two copies of the form, and the coordinator will also sign the consent form. One copy of the form will be kept; one copy will be given to the parent/guardian.

Teen Assent. Assent will be obtained in a similar manner as the informed consent. The assent form will be written using language that is developmentally appropriate. Adolescents will be told that they do not have to answer any questions they do not wish to, and they are free to stop being in the study at any time. Adolescents will be asked to read the assent form silently while the coordinator reads the assent form to them.

b) Vulnerable populations: The coordinator will solicit and answer questions. To make certain of their understanding of the assent consent, adolescents will be asked to explain back what they are being asked to do and clarification will be provided.

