5. SUBJECT WITHDRAWALS

Participants will be withdrawn from the study if they become pregnant or incarcerated as described above. In addition, those who do not show up at the camp or misses 3 or more assessment points in a row will be withdrawn from the study. For peer leaders, if they do not complete the three training sessions, they will become disqualified. Those disqualified peer leaders, however, can continue their participation as regular teen subjects (campers) if they are 16-17 years, after re-consenting as a camper.

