10. DATA ANALYSIS AND DATA MONITORING

10.1 Planned Statistical Analysis: Analyses will be performed using SAS, and R⁵⁶ will be used as analysis software to ensure the validity and reproducibility of the results. We will perform descriptive statistics on each outcome measure to look for abnormality and outliers. If a measure is not normally distributed, transformation will be applied. We will identify and investigate outliers for sources of errors, and conduct preliminary analyses on data distribution and bivariate correlations to determine the appropriate statistical model as well as the final interpretation of the results. We will investigate missing data with pattern analysis for data missing completely at random (MCAR), missing at random (MAR) or missing not at random (MNAR), and use statistical methods appropriate for each type such as maximum likelihood and multiple imputation to impute missing values so full analysis can be performed with sensitivity. We will compute Cronbach's alphas for psychometric measures, and assess construct validity using exploratory or confirmatory factor analysis when appropriate. The PLASMA and control groups will be compared on baseline data to determine any systematic differences; if any are found, analyses will include the variables as covariates in the model to adjust for the imbalances.

Aim 1: A multi-site hierarchical three-level linear mixed-effects model,^{26, 56, 57} where level 1 represents repeated measures, level 2 = subject, and level 3 = site, will be used to analyze treatment differences and treatment-by-time interaction described in the following notation by Hedeker and Gibbons.⁵⁷

Aim 2: The mediating effects will be examined mainly using the mediation methods of Baron & Kenny.⁵⁸ When found significant, a multiple mediation analysis⁵⁹ procedure will be used to further determine whether the effect of PLASMA on quality of life is mediated jointly by multiple exploratory outcomes.

Aim 3: Moderating effects will be examined by multiple linear models and generalized linear models described in Berridge and Crouchley⁵⁶ or Chen and Peace⁶⁰ along with the above multi-site hierarchical three-level linear mixed-effects models.

Aim 4: This aim will be tested by applying the multi-site hierarchical two-level linear mixed-effects models described in the analysis for Aim 1, with level 1 representing longitudinal measurements and level 2 sites.

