Aim 5: The costs of services received during visits to a physician's office, outpatient department, or ED will be estimated by taking the global relative value unit for each service CPT (Current Procedural Terminology) code multiplied by a standard conversion factor.⁶¹ Hospital charges will be converted to costs using department-specific cost-to-charge ratio.⁶² Medications and dosages prescribed will be captured; standard wholesale unit cost from the Pharmaceutical Red Book⁶³ will be used to estimate medication costs. To calculate lost productivity costs of a family with a sick teen, we will estimate total lost income related to each participant by multiplying total number of work hours missed by a parent's hourly wage. Program costs will be estimated from the actual time peer and adult leaders spent in carrying out the program multiplied by hourly earnings, costs of equipment/ supplies, and overhead costs; program time will not include staff time for research-related tasks. We will estimate the average program cost per participant by study group, and include this estimate as one component of direct healthcare costs. The

medical or general Consumer Price Index⁶⁴ will be used to inflation-adjust costs to current year prices.⁶⁴ For each teen at each time-point, we will calculate total direct costs, direct costs by major category (office visit, hospitalization), indirect lost-productivity costs, and total direct and indirect costs. For withdrawals from follow-up, we will impute missing utilization and cost data assuming a linear trend in use and cost given prior experiences, where we will estimate weighted least square regression on log-transformed cost and obtain smearing-retransformed predictions.⁶⁵ For PLASMA and control groups separately, we will calculate the cost difference between each time point and baseline for each teen, assuming (s)he received “standard care” before treatment. Cost differences for each group will be modeled against follow-up points and individual covariates to estimate the independent impacts of each program on costs relative to standard care.

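### Destroying all data of anyone who asks to withdraw erases randomised teens from the primary analysis and leaves the missing-data and cost-imputation steps with no input for them

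*Combined protocol and SAP*

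**What the plan says.** The destruction rule appears in the same words in Section 7 (Confidentiality paragraph) and Section 8: "All data from any parent or adolescent requesting withdrawal from the study will be destroyed at the time of the request". Neither place makes an exception for data already collected, for the randomisation record or for adverse event records. Section 3.2 tells families that "they are free to withdraw from the study at any time".

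Section 5 describes a separate route, in which the study removes the participant. Besides pregnancy and incarceration, "those who do not show up at the camp or misses 3 or more assessment points in a row will be withdrawn from the study". No destruction is attached to that route.

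Section 10.1 sets out the analysis. The Aim 1 model is hierarchical, "where level 1 represents repeated measures, level 2 = subject, and level 3 = site". On missing data, "We will investigate missing data with pattern analysis for data missing completely at random" (and for the other two mechanisms), and the team will "use statistical methods appropriate for each type such as maximum likelihood and multiple imputation to impute missing values". For costs under Aim 5, "For withdrawals from follow-up, we will impute missing utilization and cost data assuming a linear trend in use and cost given prior experiences".

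**The concern.** A request to withdraw comes after randomisation and may be related to both arm and asthma status. The arms attend separate camps, meet different leaders and receive contacts on different topics, so the reasons for leaving can differ by arm. Normally a likelihood-based mixed model limits the damage: a teen who leaves after four assessments still contributes four quality-of-life scores, and the estimate is valid if dropout depends only on what was observed. Once the record is destroyed, the model has nothing to condition on. The analysis becomes one of teens whose families did not ask to leave. The baseline data that would show whether leavers differed from stayers have gone too.

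Destruction cannot be undone, so no later sensitivity analysis based on those teens' own data can repair it.

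**Working it through.** **1. The rule against the analysis steps.** For a randomised teen who asks to withdraw after some assessments:

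| Planned step (Section 10.1) | What it needs | What remains |
|---|---|---|
| Aim 1 three-level mixed model | at least one outcome row | none; no contribution to the likelihood |
| Missing-data pattern analysis | observed and missing rows for the teen | none; the teen fits no pattern |
| Maximum likelihood or multiple imputation | baseline or earlier scores | none |
| Baseline comparison of the arms | baseline values | none; the arms compared are those left after erasure |
| Aim 5 cost differences from baseline, and cost imputation | the teen's own baseline and earlier costs | none |

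The clash with Aim 5 is the most direct, because that step is written for withdrawals and extrapolates from each one's own history. Nothing in the plan says how erased randomised teens are to be counted.

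**2. The plan's own sample size.** Section 2.1(a) says: "These estimated values with a Type-I error rate (alpha) of .05 yielded a total sample size of 276", with power .80, then allows for 27% attrition. 276 / (1 − 0.27) = 276 / 0.73 = 378.08, which reproduces the stated 378. In reverse, 378 × 0.73 = 275.9. The 27% is the earlier inner-city subsample's loss: (13 + 2) / 55 = 27.3%, made up of 13 camp no-shows and 2 lost to follow-up. Neither is a count of withdrawal requests.

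**3. How many teens could be erased.** The documents give no request rate, so this range is assumed:
- 2%: 378 × 0.02 = 7.6, about 8 teens
- 5%: 378 × 0.05 = 18.9, about 19 teens
- 10%: 378 × 0.10 = 37.8, about 38 teens

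**4. Power.** If requests fall within the 27%, about 276 teens remain and power is about .80. If they come on top of it, power can be scaled from the plan's own anchor of .80 at 276. With two-sided alpha of .05 (sidedness is not stated, so this is assumed), power = Φ[(1.960 + 0.842) × √(N/276) − 1.960]:
- 2% on top: N = 378 × 0.71 = 268.4, power .79
- 5% on top: N = 378 × 0.68 = 257.0, power .77
- 10% on top: N = 378 × 0.63 = 238.1, power .74

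**5. Bias, for illustration only.** Suppose requesters differ from the rest of their arm by g in the outcome, with g the same in both arms. Erasing a share w of an arm shifts that arm's mean by w × g, so the arm difference shifts by (w₁ − w₂) × g. With assumed shares of 10% and 5%:
- g = 5 points: 0.05 × 5 = 0.25
- g = 15 points: 0.05 × 15 = 0.75

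The trial was sized on the treatment-by-time coefficient, so the same formula is also useful on slopes. If requesters' slopes differ by 1.76 (the plan's random-slope figure, read as an SD), the shift is 0.05 × 1.76 = 0.088. Against the design effect of 0.6 this is 0.088 / 0.6 = 15%. Equal shares give no shift under this formula, but only while g is the same in both arms.

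**The case against.** Several points on the other side carry weight.

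*The missing-data plan mostly still works.* A reader might infer that it fails for dropouts in general. The documents do not support that. Teens removed under Section 5 and teens lost to follow-up have no destruction rule, so their earlier data stay and every step in Section 10.1 can be run for them. The conflict covers requesters only.

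*Safety reporting has its own channel.* A reader might infer that adverse events of those who leave are lost to the safety committee. Section 6 has staff report events immediately to the PI and site-PI, has the PI discuss them with the committee, and sends them to the IRBs within 7 working days (1–2 for camp events). Nothing says that those reports are recalled, so they would probably survive. What stands is that the rule, read literally, reaches the study's own adverse event records, and its scope there is not stated.

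*The size is unknown.* The 2 of 55 in Section 2.1(a) is loss to follow-up, a different event, and cannot serve as a request rate. Section 3.2 says assignment is concealed from participants, so reasons tied to the leaders or the contacts would arise mainly from the camp onward. In the earlier subsample, 13 of the 15 losses were camp no-shows. Requests may be few.

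*Destruction on request is a privacy commitment to minors and their parents.* That is a legitimate aim. However, Section 8 already keeps identifiers apart from coded data, so most of the protection can be kept without erasing coded results.

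**Conclusion.** The point holds for participants who ask to withdraw. The text is explicit, appears twice and has no exception. It is incompatible with the cost imputation for such teens and removes them from the Aim 1 model and the missing-data work. The result is a post-randomisation exclusion that may depend on arm and whose bias cannot be assessed.

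The conflict in the text is certain; its size is not. The range of about 8 to 38 teens rests wholly on an assumed 2% to 10% request rate, and the bias figures rest on assumed differences between requesters and others. A reader might infer that the trial would be underpowered or that 378 is too small. The documents do not support this: 378 follows from 276 and 27%, and power stays near .80 unless requests come on top of the allowance, where the assumed range gives .74 to .79.

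**What to change.** In Sections 7 and 8, and in any matching consent and assent text (not available for this review), replace the destruction rule with wording such as:

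*On a request to withdraw, no further data will be collected; coded data and adverse event records collected up to that date are kept and analysed in the arm to which the teen was randomised.*

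Three details need to go with it.
- **Claims and records.** Costs come from purchased Medicaid claims and medical records (Section 4.1), which must be matched to individuals. State whether items dated before the request may still be obtained, and remove the identity link only after any permitted matching is complete. Removing it at once could leave the Aim 5 imputation without input again. Section 8 also places a link to the subject ID on the consent documents, so say how those are handled.
- **Who is covered.** Apply the new rule to participants who consent under it. For anyone enrolled under the existing promise, follow IRB direction.
- **Reporting.** Give the number of erased participants by arm in the participant flow.

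The cost is an IRB amendment with revised consent and assent wording, and a less absolute privacy promise, partly offset by the later removal of the identity link. The sample size does not change.
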